5.4.4. Reader Selection

The readers will be a mixture of general radiologists and breast imaging subspecialists to reflect the pool of potential users in clinical practice. All readers will be MQSA-qualified, ABR Board-certified radiologists. The readers' experience level with reading tomosynthesis images will be documented.

The following inclusion criteria must be met for readers:

- MQSA qualified radiologist
- ABR Board Certified
- At least 2 years in clinical practice including interpretation of digital mammograms
- All potential readers must complete the Philips tomosynthesis training and test session in order to be a valid reader in the actual study.

The radiologists will provide the following documentation in support of determining their eligibility reader study coordinator and maintained in the reader's study folder:

- Curriculum Vitae
- Medical License
- Qualification Survey which will record the name and address of their radiology practice, the years of experience in interpreting digital mammograms.

Documentation of completion of Philips tomosynthesis training by each reader will be included in the reader's study folder kept on site with a copy in the Philips study master file.

5.4.5. Reader Training

The goal of the reader training sessions is to assure that the readers are sufficiently trained in the interpretation of Philips tomosynthesis images. Training will be conducted by an expert radiologist with an application specialist experienced in the softcopy review workstation operation will be on hand to assist readers with use of the review workstation in order for the readers become familiar with its functionality.

The training will consist of two parts, Part 1: an initial overview of tomosynthesis and synthetic 2D presented by radiologist training with subsequent discussion of a series of 20 training cases and Part 2: Independent review by the reader of 30 additional cases.

5.4.5.1. Part 1 Training

The training data set will consist of 10 biopsy-proven cancer cases (5 calcifications, 5 mass) and 10 biopsy-proven benign lesions (5 calcifications, 5 mass) cases and 10 normal cases. During the initial review, the cases will be presented side by side for comparison of tomosynthesis and synthetic 2D and FFDM images. The trainer will point out the range of typical anatomy and abnormalities identified with tomosynthesis. Training will also include protocol procedure training on reading images from

tomosynthesis and FFDM systems, review station software tools, instructions for use of the Confidence Scales, instruction regarding completion of the Case Report Forms (CRFs) and a hands-on session at the review workstation to provide the Readers with an overview of their functionality and standard image review tools for tomosynthesis and FFDM viewing. Reader trainees will also be given written instructions on image interpretation, which they may refer to during the training sessions.

5.4.5.2. Part 2 Training

After this initial training, all readers will be required to independently review and score thirty tomosynthesis and synthetic 2D case sets. These sets will consist of 10 malignant cases, 10 benign cases, and 10 normal cases and complete the CRFs. Following the independent read of this case set, a study assistant will review the reader's completion of all CRFs in training to make sure they understand the process.

No cases used in training will be used in the reader study.

5.4.6. **Case Selection**

5.4.6.1. Selection of Normal Cases

A normal – no recall case is defined as a case classified as BIRADS 1 or 2 by initial screening clinical reporting from the sites with confirmation that no cancer has been diagnosed after 1 year of follow-up past enrollment to the study. A normal – recall case is defined as a case classified as BIRADS 1 or 2 after completion of the diagnostic workup following an abnormal screen triggering recall.

A total of approximately 300 normal cases, 270 normal-no recall and 30 normal-recall will be sequentially selected by the statistician from all cleared cases which approximately represents the distribution of breast densities in the general population, including almost entirely fatty, scattered fibroglandular elements, heterogeneously dense and extremely dense breast as presented in Table 2.

Stratification criteria	Target	Min (-30%)
Breast density		
A: Almost entirely fat	11% / 32	22
B: Scattered fibroglandular densities	43% / 129	90
C: Heterogeneously dense	39% / 117	82
D: Extremely dense	7% / 22	16

Table 2: *Stratification Criteria for Normal Cases (n=300) in accordance with [6]*

5.4.6.2. Selection of Cases that are benign at biopsy

In addition, cases that were benign at biopsy will be selected among those cases that had benign proven biopsy. A biopsy benign case is defined as a case for which the subject undergoes biopsy of one or more breast lesions that were all determined pathologically to be benign with confirmation of non-cancer status after 1 year of follow-up past enrollment of the study.

27 benign cases (by imaging) will be sequentially selected by the statistician from all cleared cases which approximately represents the distribution of breast densities in the general population, including almost entirely fatty, scattered fibroglandular elements, heterogeneously dense and extremely dense breast. Both mass and calcifications findings type will be included.

13 biopsy benign cases will be sequentially selected by the statistician from all cleared cases which approximately represents the distribution of breast densities in the general population, including almost

entirely fatty, scattered fibroglandular elements, heterogeneously dense and extremely dense breast. Both mass and calcifications findings type will be included. One year follow-up will be documented prior to the final statistical analysis. The stratification for benign cases is presented in Table 3.

Stratification criteria	Target	Min (-30%)
Lesion type		
Calcification	43% / 17	12
Mass	57% / 23	16
Breast density		
A: Almost entirely fat	11% / 4	3
B: Scattered fibroglandular densities	43% / 17	12
C: Heterogeneously dense	39% / 16	11
D: Extremely dense	7% / 3	2

Table 3: Stratification criteria Benign Cases (n=40)

5.4.6.3. Selection of Cancer Cases

The final classification of a cancer case for potential inclusion in the reader study will be performed by an expert radiologist. The expert radiologist will be provided with the Philips MicroDose tomosynthesis system images, digital mammograms, and relevant clinical data including confirmation of a positive biopsy for cancer. The expert radiologist will record the visibility and location of the lesion on the CRF.

65 positive cases will be selected to represent an enriched sample similar to the distribution of cases in a screening population which might be seen in clinical practice in the U.S. regarding lesion type, breast density distribution, and lesion size as presented in Table 4.

Stratification criteria	Target	Min (-30%)
Lesion type		
Calcification	37% / 24	17
Mass	48% / 31	22
Architectural distortion or asymmetry	15% / 10	7
Breast density		
A: Almost entirely fat	11% / 7	5
B: Scattered fibroglandular densities	43% / 28	20
C: Heterogeneously dense	39% / 25	18
D: Extremely dense	7% / 5	3
Lesion size		
Minimal cancer (≤ 10 mm or DCIS)	52.7% / 34	24

Table 4: Stratification criteria CANCER CASES (n=65)

Philips Mammography Solutions Sweden	Clinical Investigation Plan Comparison of the Philips MicroDose Tomosynthesis System to 2D Digital Mammography	DOC-MTIN-9RWH8K- 8.0 Page 22 of 38
---	---	--

5.5. Endpoints

5.5.1. Clinical Endpoint: Image Accrual Phase

For all participating subjects, the following information, as applicable will be collected during the imaging acquisition and recorded on the case report form (CRF):

- Demographics: Date of informed consent, date of birth, race, ethnicity, and menopausal status
- Medical History
- Breast Imaging-Reporting and Data System (BI-RADS) score will be performed by the interpreting radiologists for both the Philips MicroDose tomosynthesis mammograms and the FFDM. The following ratings will be used:
 - 0 – Incomplete,
 - 1 – Negative,
 - 2 – Benign finding(s),
 - 3 – Probably Benign,
 - 4 – Suspicious abnormality,
 - 4 a - Low suspicion for malignancy
 - 4 b – Moderate suspicion for malignancy
 - 4 c – High suspicion for malignancy
 - 5 – Highly suggestive of Malignancy
- Screening Population cases will be classified as No Recall if both Tomo and FFDM exams have final assessment of BIRADS 1 or 2. Screening population cases will be classified as Recall if either Tomo or FFDM exam is classified as BI-RADS 0, requiring additional diagnostic imaging workup.
- Screening population cases that were recalled, 0, for additional diagnostic work-up must have a final BIRADS assessment of 1, 2, 3, 4a, 4b, 4c, or 5.
- The study imaging standard exam (Tomo or FFDM) that is performed prior to biopsy in the biopsy cohort arm must be interpreted and assigned a final BIRADS assessment of 1, 2, 3, 4a, 4b, 4c, or 5. Breast density score: The breast density score will be performed at the acquisition site by at least one radiologists using the standard of care FFDM images. Cases will be categorized using BI-RADS breast density scale as either non-dense (BI-RADS breast density type A or B) or dense (BI-RADS breast density type C or D).
- Whether the case is scheduled for a screening mammogram or a biopsy
- Lesion type: Lesion type will be defined at the acquisition site using BI-RADS scale and classified as mass, calcifications, asymmetry, or architectural distortion.
- Biopsy results
- Images from the screening examination for the screening cohort

5.5.2. Clinical Endpoint: Image Reading Phase

The Readers will independently review Philips MicroDose Tomosynthesis images and FFDM screening mammogram for each case in two separate reading sessions separated by a wash-out period of at least one month. The cases to be included in the reader study will be divided into two groups with an equal number of cancer cases and an equal number of FFDM and tomosynthesis exams in each group.

The review of FFDM exams will include reading the standard bilateral 2-view mammograms (CC and MLO). The review of Tomosynthesis will include reading of the Tomosynthesis (CC and MLO) plus synthesized 2D images (CC and MLO) generated from the tomosynthesis images. No patient history

Philips Mammography Solutions Sweden	Clinical Investigation Plan Comparison of the Philips MicroDose Tomosynthesis System to 2D Digital Mammography	DOC-MTIN-9RWH8K- 8.0 Page 23 of 38
---	---	--

or other clinical information will be provided to the Readers. The following data points will be collected using case report forms which will be completed directly by the readers:

- Forced BI-RADS score of 1, 2, 3, 4a, 4b, 4c, or 5
- Confidence Score (CS): Readers will be asked to assign a confidence score for the BI-RADS ratings as follows: For BI-RADS 3 to 5, the confidence score represents the reader's interpretation of the likelihood of the lesion being malignant on a scale of 51 to 100. The score 51 represents the least suspicious Recall case, whereas the score 100 represents the most suspicious Recall case. For BI-RADS 1 or 2, the confidence score represent the reader's confidence that the case is normal and will range from 1 to 50. The score 1 represents the most normal No-Recall case, whereas the score 50 represents the least normal No-Recall case. For the per-case ROC analysis, the confidence score for the case will be the overall score documented by the reader.
- Readers will mark all lesions by location (breast and clock location).
- For the FROC analysis, each lesion or foci identified by the reader will rated using a confidence score that the abnormality in question representing a cancer "if it was actually present". For this analysis confidence score will range from 1 to 100. A research associate (RA) located at the reader study facility will check the progress of the readers during each reading session. The RA will also check for missing data elements on the form and check all cases for completeness for each group of cases during the reading session. The RA will generate a query list to resolve any missing data points or cases prior to the reader ending a session. The RA will also assist readers with workstation problems and CRF issues should they arise.

5.5.3. Procedure Endpoint

- Radiation dose: Average Glandular radiation dose will be read out from the DICOM header for each mammogram.
- Image interpretation time: Interpretation time will be measured during the reading study for each reader. The interpretation time includes the time the reader takes reviewing the case and completing the case report form.

5.5.4. Safety Endpoint

- All expected or unexpected adverse events will be reported.

5.6. Monitoring Plan

Monitoring will be performed by a trained person appointed by Philips to ensure compliance with the Clinical Investigation plan, applicable national regulations and international standards, patient safety and data validity. The Sponsor may designate one or more individuals to monitor the progress of a clinical study. The Sponsor may also delegate the monitoring responsibilities to a third party. However, the Sponsor remains ultimately responsible for the conduct of the study. The Institution is responsible for the appropriate de-identification of subject data. The investigational site should provide access to the source data of the subjects.

The monitor selected by the Sponsor will visit each site prior to study start and periodically during data collection phase. During each visit the monitor will review subject records including informed consent forms and case report form data. After each visit an on-site report will be written. A close-out visit for sites that have enrolled subjects will be conducted once the site has completed collecting data for the study.

Philips Mammography Solutions Sweden	Clinical Investigation Plan Comparison of the Philips MicroDose Tomosynthesis System to 2D Digital Mammography	DOC-MTIN-9RWH8K- 8.0 Page 24 of 38
---	---	--

The monitor will ensure that all adverse device effects (anticipated and unanticipated) and complaints are reported to the sponsor in a timely manner and that unanticipated adverse device effects are reported to the IRB.

A detailed plan for monitoring arrangement will be available separate from this protocol.

Names of the monitor(s) can be found in *Appendix II: List of monitor(s)* of this protocol. An update of this list can be provided to the site under separate cover.

5.7. Deviations from the clinical plan

The Investigator is not allowed to deviate from the Clinical Investigation Plan or to enroll subjects that do not comply with all inclusion and exclusion criteria. Under emergency circumstances, deviations from the Clinical Investigation Plan to protect the rights, safety and well-being of human subjects may proceed without prior approval of the sponsor and the EC. Such deviations shall be documented and reported to the sponsor and the EC as soon as possible.

All deviations from the Clinical Investigation Plan will be documented with date, subject, reason, actions taken and if the deviation affects subject's rights, safety and wellbeing or the scientific integrity of the clinical study. The deviation shall be notified to the Sponsor as soon as possible via the CRF. Deviations will be reviewed by the sponsor and in case of serious or repetitive deviations a corrective action plan may represent a need to initiate a corrective action plan with the principal investigator. In some cases, necessitate suspension of enrollment at the site or ultimately the principal investigator will be disqualified.

6. STATISTICAL CONSIDERATIONS

6.1. Sample Size and Number of Readers Justification

6.1.1. Sample Size Justification for Primary Efficacy Analysis

The primary endpoint is the Receiver Operator Characteristics curve analysis for both tests. In this trial, the 2D is the control test, and the tomosynthesis and synthetic 2D is the experiment test. The plan is to enroll approximate 800 patients, to include 65 patients with cancer, 40 biopsy-proven benign cases and 300 normal cases. The evaluations will be based on paired-cases and paired-readers that is all readers will interpret the test results of all patients in both tests (i.e., Philips MicroDose tomosynthesis system and FFDM).

The sample size (number of readers) for the Reader Study is estimated based mixed-effects model for the diagnostic accuracy of a reader j using a particular diagnostic test i on reading occasion q as proposed by Obuchowski [11]. The mixed model is specified as follows:

$$\hat{\theta}_{ijq} = \mu + \mu_i + r_j + (ur)_{ij} + \epsilon_{ijq}$$

Here, $v_i = \mu + \mu_i$ is the mean accuracy of test i (fixed effect), r_j is a random effect for reader j , $(ur)_{ij}$ is an interaction term for readers and tests (random effect), and ϵ_{ijq} is an error term.

An F-statistic with 1 and $(J-1)$ degree of freedom (df) will be used for testing the null hypothesis that the mean diagnostic accuracies of the tests are equal, where J is the number of readers. Under alternative hypothesis, the test statistic follows a non-central F distribution with 1 and $(J-1)$ df, and the non-centrality parameter is estimated as following:

$$\hat{\lambda} = \frac{J(\mu_1 - \mu_2)^2}{2\{\hat{\sigma}_b^2(1 - \hat{\rho}_b) + \frac{\hat{\sigma}_w^2}{Q} + \hat{\sigma}_c^2[(1 - \hat{\rho}_1) + (J - 1)(\hat{\rho}_2 - \hat{\rho}_3)]\}}$$

Philips Mammography Solutions Sweden	Clinical Investigation Plan Comparison of the Philips MicroDose Tomosynthesis System to 2D Digital Mammography	DOC-MTIN-9RWH8K- 8.0 Page 25 of 38
---	---	--

Thus, to calculate the statistical power, multiple parameters in the equation above need to be estimated. For this study, these estimates are based on the following assumptions:

- The type I error: $\alpha = 0.05$
- AUC for control test: $A = 0.85$
- Number of positive patients: $n_1 = 65$
- Number of negative patients: $n_2 = 300$
- Non-inferiority margin: $\Delta = 0.05$
- Variability between readers: $\sigma_b^2 = 0.0009$
- Variability within the reader: $\sigma_w^2 = 0.000225$
- Correlations: $\rho_1 = 0.46$, $\rho_2 - \rho_3 = 0$
- Correlation: $\rho_b = 0.5$
- Power for the non-inferiority test: $1 - \beta \geq 0.8$

The variance between different patients σ_c^2 will be calculated based on the method of Obuchowski (1994). It is suggested that for the ROC analysis, σ_c^2 can be obtained as follows.

$$\sigma_c^2 = \frac{0.0099 \times e^{-\frac{a^2}{2}} \times [5a^2 + 8 + (a^2 + 8)/R]}{n_1}$$

Where $a = \Phi^{-1}(A) \times 1.414$ and Φ^{-1} is the inverse of the cumulative normal distribution function; n_1 is the number of positive patients; and R is the ratio of the number of negative patients (n_2) to positive patients (n_1).

The assumed AUC for control test (A) is 0.85. In a previous study on the Philips L30 system, the area under the ROC curve was 0.947, with a 95% C.I. (0.920, 0.974)[19]. In another similar study for the Hologic Tomosynthesis Mammography System, the AUC based on Probability of Malignancy for a 2D system is 0.867 [20]. Therefore for this study it is expected that the AUC for the control test will be approximately 0.85.

The variance between readers interpreting the same patients σ_b^2 is based on a study performed by Beam, Layde and Sullivan [16]; and it was widely used in previous studies. In a previous study on Philips L30 system [19], the estimated σ_b^2 with 95% C.I. is 0.0005 (0.0003, 0.0013), thus a value of 0.0009 is a reasonable estimation for σ_b^2 in the proposed study.

The variance within each reader interpreting the results of the same patients σ_w^2 is estimated as one-fourth of σ_b^2 , thus 0.00025.

The four correlations are usually estimated from a pilot study or previous studies. Correlation for the same patients evaluated by the same reader using different tests (ρ_1), for the same patients evaluated by different readers with the same tests (ρ_2) and for the same patients evaluated by different readers and different tests (ρ_3) are based on suggestions from Obuchowski [11]. The correlation for the same reader to evaluate patients using different tests ρ_b ranges from 0.44 to 0.86, based on Rockette et al. (1999). It is assumed that a correlation equal to 0.5 is a conservative estimate.

Based on these values, 18 readers will be required to achieve statistical power of at least 0.80.

Philips Mammography Solutions Sweden	Clinical Investigation Plan Comparison of the Philips MicroDose Tomosynthesis System to 2D Digital Mammography	DOC-MTIN-9RWH8K- 8.0 Page 26 of 38
---	---	--

6.1.2. Sample Size Justification for Average Glandular Dose

Another secondary objective of this study is to compare the average radiation dose between the Philips MicroDose tomosynthesis system and FFDM systems. Radiation dose will be evaluated based on the subject overall dose received during the examination. For the null hypothesis, no difference in radiation dose delivered to the patient during a mammographic exam between two systems, will be evaluated.

Using historical data from the study site, the average radiation dose per breast for 20 subjects, 2 sample (MLO + CC) was of 3.6 (standard deviation of 1.1), ranging from 2.4 to 6.7 for the GE FFDM, and of 2.6 (standard deviation of 0.7) ranging from 1.6 to 4.0 for Hologic mammography system. Also, in a previous study, comparing the three systems reported radiation dose per breast of 1.86, 2.91, and 3.03, for Philips MicroDose, Hologic and GE, respectively representing a reduction of radiation of approximately 40% for MicroDose compared to Hologic and or the GE mammography system.

Assuming that the standard deviation for the difference in radiation dose will be approximately 1.5mGy, a sample size of approximately 100 subjects will allow for greater than 80% power to detect a difference in radiation between the two systems of approximately 0.5mGy (i.e., 10% of the overall patient radiation) using a paired t-test with a 0.025 one-sided significance level.

6.1.3. Sample Size Justification for Recall Rate

Based on the outcome of the most recent tomosynthesis PMA (i.e., MAMMOMAT Inspiration with Tomosynthesis, P140011), the recall rate for A FFDM alone was 0.438. For this study, a similar recall rate is expected. Assuming that a 5% reduction in recall rate for tomosynthesis is clinically significant and adjusting for the multiple endpoints, a total of 2300 cases will allow for approximately 80% to detect an improvement in recall rate of approximately 5%. Furthermore, assuming that the correlation among readers reading the same case in approximately 0.5, and that all subject will be read by all 18 readers, approximately 250 subjects will be required.

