Analysis will be performed using an appropriate analysis of variance. If the required assumptions for the ANOVA are violated, transformation of the data or non-parametric procedures may be used. The 95% confidence interval for the mean difference in radiation dose between the two systems will be constructed. Under this proposal Philips tomosynthesis will be declared as emitting less radiation than the FFDM if the upper bound of the 95% confidence interval for the difference in radiation dose is less than 10% of the FFDM.

The non-cancer recall rate will be recorded per subject. All negative screening, recalled and benign biopsy cases will be included. The following hypothesis will be evaluated:

- Null Hypothesis: $H_0: \pi_2 - \pi_1 = 0$
- Alternative Hypothesis: $\pi_2 - \pi_1 \neq 0$

where π_1 and π_2 are the non-cancer recall rate for the Philips MicroDose Tomosynthesis system and FFDM system, respectively.

Recall rate will be analyzed using the concept of clustered binary data as described by Zhou et al (2011). In this case, each Reader will be considered as multiple observations within the same subject (cluster). The 95% confidence interval for the difference in recall rate will be constructed. If the upper limit to the one-sided 95% Confidence Interval for the difference (Philips minus FFDM) in recall rates among non-cancers is less than 0.05 (delta of 5%), Philips tomosynthesis will be considered as resulting in a similar recall rate to that of 2D FFDM. In addition, a bootstrapping method with replacement will be used to compare average recall rates among all Readers.

The sensitivity or specificity within a reader between the two systems will be estimated, and tested for statistical significance using binomial test for paired data. Results will be summarized across readers using the ANOVA model of Obuchowski and Rockette [11], which applies to any metric of diagnostic accuracy under general conditions. The following hypothesis will be evaluated:

- Null Hypothesis: $H_0: S_2 - S_1 \geq 0.10$

Philips Mammography Solutions Sweden	Clinical Investigation Plan Comparison of the Philips MicroDose Tomosynthesis System to 2D Digital Mammography	DOC-MTIN-9RWH8K- 8.0 Page 31 of 38
---	---	--

- Alternative Hypothesis: $S_2 - S_1 < 0.10$

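### Recall-rate sample size (6.1.3): about 250 subjects does not follow from 2300 cases, 18 readers and a correlation of 0.5, so the roughly 80% power is not demonstrated, and the planned recall analysis omits reader variance

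*Combined protocol and SAP*

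**What the plan says.** Section 6.1.3 takes an FFDM recall rate of 0.438 and treats a 5% reduction as clinically significant. After an unspecified adjustment for multiple endpoints, it states that "a total of 2300 cases will allow for approximately 80% to detect an improvement in recall rate of approximately 5" percent. It continues "assuming that the correlation among readers reading the same case in approximately 0.5", and concludes that, since "all subject will be read by all 18 readers, approximately 250 subjects will be required", the study is large enough. It prints no conversion formula, numeric alpha, between-modality correlation or reader variance.

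The design is fully paired: section 6.1.1 says "all readers will interpret the test results of all patients in both tests". Section 5.3.4 plans about 300 normal and 40 benign cases, which gives 340 non-cancers.

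Section 6.8 sets a two-sided hypothesis of no difference in recall and analyses it as clustered binary data, where "each Reader will be considered as multiple observations within the same subject (cluster"). Its decision rule is that the upper one-sided 95% limit for the difference, Philips minus FFDM, "in recall rates among non-cancers is less than 0.05 (delta of 5" percent). It adds that "a bootstrapping method with replacement will be used to compare average recall rates among all Readers", without naming the resampling unit. For sensitivity and specificity the same section uses the Obuchowski-Rockette model, "which applies to any metric of diagnostic accuracy under general conditions".

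**The concern.** There are three linked problems.

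- **The conversion.** Eighteen readings of one case, correlated at 0.5, carry far less information than eighteen independent readings. Going from 2300 to 250 keeps nearly all the credit for multiple readers and almost none of the penalty for correlation.
- **The analysis.** Clustering on subject handles correlation among readers of the same case but treats the 18 readers as fixed. Reader-to-reader variation in the modality difference does not enter the interval. Yet section 5.4.4 selects readers to reflect the pool of potential users, and the AUC, sensitivity and specificity analyses all treat readers as random.
- **The target.** Section 6.1.3 powers an improvement, the hypothesis in 6.8 is a two-sided difference, and the decision rule in 6.8 is a margin of +0.05.

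At stake are a stated sample size and power that cannot be relied on, and a recall interval too narrow for any claim beyond these readers. Recall is also one of the two endpoints whose rejection opens the sensitivity and specificity tests. Dose alone can open them too, so the effect on the testing sequence is partial.

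**Working it through.** **Inputs.** From 6.1.3: recall 0.438 against 0.388, 18 readers, correlation 0.5, 2300 cases, 250 subjects. From 5.3.4: 340 non-cancers. From 6.1.5, where recall has no values of its own: same-reader between-modality correlation ρ1 = 0.46, reader variance 0.012, within-reader variance 0.003, ρb = 0.8. The 6.1.5 values were chosen for specificity, so using them for recall is an assumption.

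**Step 1: the 2300.** An unpaired two-proportion comparison at 80% power needs, per modality:

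| Two-sided alpha | Reads per modality |
|---|---|
| 0.05 | 1,522 |
| 0.025 | 1,843 |
| 0.01 | 2,264 (2,304 with continuity correction) |

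The best match is therefore 2300 per modality at 0.01. As a total over both modalities, the nearest match is 2,396, at one-sided 0.05. Alpha is not printed, so both readings stay open.

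**Step 2: the 250.**
- Design effect = 1 + (18 − 1) × 0.5 = 9.5.
- Subjects = 2300 × 9.5 / 18 = 1,214. If 2300 spans both modalities, 1150 × 9.5 / 18 = 607.
- Correlation that would give 250: (18 × 250 / 2300 − 1) / 17 = 0.056, or (18 × 250 / 1150 − 1) / 17 = 0.171.
- Numbers near 250 arise from 2300 / (18 × 0.5) = 256 and 2300 / 9.5 = 242. Neither is a valid conversion.

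**Step 3: power with pairing.** The target is a 5-point reduction, two-sided test, power = Φ(0.05/SE − z). Results are given at alpha 0.05 / 0.025, since Holm over two endpoints puts recall between these levels.

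*Readers fixed, 0.5 read as the correlation of between-modality differences.* Variance = 2 × 0.438 × 0.562 × 0.54 × 9.5 / (18n).
- n = 340: SE 0.0203, power 69% / 59%.
- n = 250: SE 0.0237, power 56% / 45%.
- 80% power needs about 433–441 / 524–534 subjects. The range depends on whether the variance uses both recall rates or 0.438 throughout.

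*Readers fixed, ρ2 − ρ3 = 0, n = 340.* Case variance = 2 × 0.438 × 0.562 / 340 × 0.54 / 18 = 0.000043, SE 0.0066, power above 99%.

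*Readers random, ρ2 − ρ3 = 0, n = 340.* Reader variance = 2 × (0.012 × 0.2 + 0.003) / 18 = 0.0006. Total SE = √(0.0006 + 0.000043) = 0.0254. Power is 50% / 39%, or 46% / 34% with the F test on 1 and 17 degrees of freedom from 6.1.1.

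**Step 4: what omitting reader variance does to the 0.05-margin rule.** Case variance = 2 × 0.438 × 0.562 / 340 × (0.54 + 17(ρ2 − ρ3)) / 18. Type I error for inference beyond these readers = Φ(−1.645 × SE clustered / SE random).

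| ρ2 − ρ3 | SE clustered | SE random | Type I error |
|---|---|---|---|
| 0 | 0.0066 | 0.0254 | 33% |
| 0.1 | 0.0134 | 0.0279 | 21% |
| 0.2 | 0.0178 | 0.0303 | 17% |

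The outer confidence limits for reader variance printed in 6.1.5 are 0.0047 and 0.0357. Keeping within-reader variance at one-fourth and ρb at 0.8, the error runs from 11% (0.0047, ρ2 − ρ3 = 0.2) to 40% (0.0357, ρ2 − ρ3 = 0).

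**The case against.** The conversion to 250 has no defence. The objections concern the size of the consequences, and several have weight.

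- **The 69% / 59% figures need a particular reading of 0.5.** The plan calls it a correlation among readers on the same case. Applying it to between-modality differences implies ρ2 − ρ3 = 0.54 × 0.5 = 0.27, whereas the plan assumes 0 wherever it states a value. If 0.5 is ρ2, readers are fixed and ρ3 is 0.3 or 0.4, power at 340 is about 80% or 96%. This stands: the calculations show missing inputs, not a measured shortfall.
- **The printed margin rule is easier to meet.** If the reduction is truly 5 points, its power at 340 with random readers is about 99%, 97% and 95% for ρ2 − ρ3 = 0, 0.1 and 0.2. If the rates are equal it is about 63%, 56% and 50%. This too stands, and shows why the powered rule must be named.
- **The Type I figures are soft.** Omitting any positive variance component pushes the error above 5%, so only its size is informative. Specificity is cut at BI-RADS 4 and recall at BI-RADS 3. More than half of the reader term (0.003 of 0.0054) comes from the one-fourth rule for within-reader variance; without it, 33%, 21% and 17% become 27%, 15% and 11%. At ρ2 − ρ3 = 0.27 the central value is 15% and the low end 9.5%. The figures are illustrative, but the direction does not change.
- **Clustering on subject is a prespecified choice, and the bootstrap could carry reader variance.** It could if readers were resampled, but the text does not say so, and the decision rule rests on the confidence limit.

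**Conclusion.** The concern holds. The step from 2300 cases to about 250 subjects is wrong on the section's own inputs: the usual design effect gives 1,214 (or 607). That is not a requirement to adopt, because it ignores the pairing. The right conclusion is that 80% power is not demonstrated, rather than shown to be missed. At 340 non-cancers and two-sided 0.05, power for a 5-point reduction lies anywhere from 46% to above 99% over the scenarios in steps 3 and 4, depending on ρ2 − ρ3 and on whether readers are random.

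The omission of reader variance from the recall interval is a separate defect and inconsistent with the plan's treatment of AUC, sensitivity and specificity. Its size rests on borrowed specificity inputs, and its direction does not. Confidence is high on the arithmetic and on the omission, and lower on the exact magnitudes. This should be fixed, but it concerns a secondary endpoint and does not touch the primary AUC analysis.

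**What to change.** In 6.1.3, delete the 250-subject statement. Restate the power of the roughly 340 non-cancer cases from a paired multi-reader calculation that gives alpha, ρ1, ρ2 − ρ3 and reader variance. State which rule is powered: the two-sided difference or the 0.05 margin. Do not insert 1,214, and do not add patients.

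In 6.8, make the Obuchowski-Rockette random-reader model the main recall analysis and keep the subject-clustered analysis as supportive. Specify that the bootstrap resamples both readers and cases. Align the recall hypothesis and decision rule with the rule powered in 6.1.3.

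The cost is wording only, with the same data, reads and software; section 6.2 already names the OR-DBM MRMC program. The price is a wider recall interval and probably a less favourable stated power.
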